Outcome of exploratory laparotomy (ex-lap) following war-related injuries has previously been extensively studied and reported on³⁻⁷. These reports have mainly concentrated on causes for and findings at ex-lap, and postoperative mortality (table 1). Few studies have focused on the differences in injury mechanism, complexity of injuries and outcome between civilians and combatants, especially in urban conflicts where IED's, human shields and suicide bombers are used².

Table 1. Findings at ex-lap and postoperative mortality in different conflicts

Conflict	Nb. of Ex-laps	Negative explorations	Small intestinal injuries	Colon injuries incl. rectum	Other injuries	Postoperative mortality
Chad,1980³	210	4,8%	33,0%	21,1%	32,7%	22,5%
Lebanon 1975-85⁴	1314	9,7%	24,7%	21,2%	55,0%	9,5%
Former Yugoslavia 1991-95⁵	93	4,3%	30,0%	28,4%	41,5%	10,8%
Gaza 2000-03⁶	230	6,5%	26,7%	17,9%	55,3%	7,4%
Mosul, Iraq, 2006⁷	153	15%	23,7%	18,7%	57,6%	33,3%

Justification

There is a need for better understanding of demographics and outcome of ex-lap following abdominal injuries sustained in urban conflicts where IEDs, human shields and suicide bombers are used. The use of these indiscriminate weapons could affect civilians to a greater extent than combatants⁸. We therefore hypothesize that the use of indiscriminate weapons in an urban setting causes more extensive abdominal injuries to the civilian population than to combatants. The knowledge gained from this study could be crucial when planning surgical staffing and facility needs in similar contexts.

Potential Risks and Benefits

Since this is an observational retrospective cohort study without any interventional methods it poses little to no harm for the participants. A potential benefit for future patients would be an increase in understanding among health care providers regarding what kind of abdominal injuries indiscriminate weapons cause. Furthermore, a better understanding of what impact the use of indiscriminate weapons has on the civilian population.

Aim of Study

To assess whether civilians have more complex abdominal injuries than combatants in an urban battle characterized by the use of indiscriminate weapons.

Primary Measure

Differences in injury mechanism, organs injured, surgical treatment given, postoperative complications and outcome between civilians *and* combatants.

Secondary Measures

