Comparison of surgical treatment given, postoperative complications and outcome between patients with prior surgical treatment of their injury *and* patients without prior surgical treatment.

Differences in surgical treatment given, postoperative complications and outcome between patients who receive surgical treatment less than 24 hours from injury *and* patients who receive surgical treatment more than 24 hours from injury will be analysed.

See chapter Data, *patient files*, for detailed primary and secondary measurements.

Investigation Plan

Study Design

A cohort study with retrospective longitudinal data collection using routinely collected clinical data.

Study Period

Consecutive patients presenting at EH between October 17, 2016 and July 16, 2017 that meet eligibility criteria will be included. Patient history information preceding hospital admission will be included.

Study Location

Emergency Hospital, Erbil, Kurdistan Region, Iraq.

Study Duration for Participants

Participants will be followed from admission until discharged from EH.

Study Population

Recruitment Methods

Patients will be included from the surgical ledger at the Surgical Department of EH.

Inclusion Criteria

- All patients treated with ex-lap due to conflict-related penetrating injury presenting at EH between October 17, 2016 and July 31, 2017 will be included.

Exclusion Criteria

- Patients who received treatment several times during the study period will only be counted as one patient.

Information for Patients and Consent

Since this study is based on data from routine care participants will not be informed, nor will consent be asked of participation, as this could introduce bias and confounding factors. There are moreover no risks or potential gains involved for participants. No incentives or inducements will be provided to any participant or staff involved.

Data

Data Sources

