- Perioperative complication (Yes/No/Unknown, specified)
- Postoperative antibiotic prophylaxis (Yes/No/Unknown, specified)
- Postoperative infection (Yes/No/Unknown, appendix 3 for definition)
- Other postoperative complication (Yes/No/Unknown, appendix 2 for definition)
- Need of postoperative intensive care (Yes/No/Unknown, specified)
- Postoperative transfusions (Yes/No/Unknown, specified)
- Use of postoperative radiology (Yes/No/Unknown, specified)
- Further surgery done (Yes/No/Unknown, specified)
- Discharge (Yes/No/Unknown, specified)
- Follow-up scheduled (Yes/No/Unknown, specified)
- Re-admission (Yes/No/Unknown, specified)
- Deceased during hospital stay (Yes/No/Unknown, specified)
- Remarks

Statistical Analyses

Sample Size

Due to the nature of the study, the sample size will be a convenience sample of the available cases during the study period. It is expected that approximately 160 subjects will be enrolled.

Statistical Methods

Analysis will be done by as treated. A 5% significance level will be used. The difference in dichotomous, such as postoperative complication (primary outcome), and categorical outcomes with more than two categories will be tested using chi-square or Fisher test. For differences in continuous variables t-test will be used. In order to adjust our analysis for possible confounders and effect modifiers we will then use linear, logistic, ordinal or multinomial regression models, according to the nature of the outcome (continuous, binary, ordinal or nominal) with injury mechanism as the dependent variable and civilian/combatant as the main explanatory variable. Important demographic and injury specific parameters such as geographical location, date, age, sex, and injured organs, will then be included in the model as potential confounders.

Safety and Monitoring

Participant Confidentiality

The use of identification numbers will ensure anonymity in the data analysis. The participant's age, gender and demographic characteristics will be used as identifying features for analysis. The research team will ensure the ethical principles of beneficence, non-maleficence, justice and respect of patients are adhered to throughout the study.

Data Collection and Management

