Appendix 1: Penetrating Abdominal Trauma Index¹⁰

Overview

The Penetrating Abdominal Trauma Index (PATI) can be used to assess the severity of injury in patients with knife, gunshot or other penetrating wounds to the abdomen. The index can be used to compare performance of different emergency care settings.

Patient evaluation

1. 14 organs are examined
2. The risk associated with injury to each organ is graded from 1 to 5.
3. The estimated severity of each type of injury is graded from 1 to 5.

Organ Injured	Risk Factor	Injury	Injury Estimate
Duodenum	5	single wall	1
		≤ 25% wall	2
		>25% wall	3
		duodenal wall and blood supply	4
		pancreaticoduodenectomy	5
Pancreas	5	tangential	1
		through-and-through (duct intact)	2
		major debridement or distal duct injury	3
		proximal duct injury	4
		pancreaticoduodenectomy	5
Liver	4	nonbleeding peripheral	1
		bleeding, central or minor debridement	2
		major debridement or hepatic artery ligation	3
		lobectomy	4
		lobectomy with caval repair or extensive bilobar debridement	5
Large intestine	4	serosal	1
		single wall	2
		≤ 25% wall	3
		>25% wall	4
		colon wall and blood supply	5

Major vascular	4	≤ 25% wall	1
		>25% wall	2
		complete transection	3
		interposition grafting or bypass	4
		ligation	5
Spleen	3	nonbleeding	1
		cautery or haemostatic agent	2
		minor debridement or suturing	3
		partial resection	4
		splenectomy	5
Kidney	3	nonbleeding	1
		minor debridement or suturing	2
		major debridement	3
		pedicle or major calyceal	4
		nephrectomy	5
Extrahepatic biliary	2	contusion	1
		cholecystectomy	2
		≤ 25% common duct wall	3
		>25% common duct wall	4
		biliary enteric reconstruction	5
Small bowel	2	single wall	1
		through-and-through	2
		≤ 25% wall or 2-3 injuries	3
		>25% wall or 4-5 injuries	4
		wall and blood supply or >5 injuries	5
Stomach	2	single wall	1
		through-and-through	2
		minor debridement	3
		wedge resection	4
		>35% resection	5
Ureter	2	contusion	1

		laceration	2
		minor debridement	3
		segmental resection	4
		reconstruction	5
Bladder	1	single wall	1
		through-and-through	2
		debridement	3
		wedge resection	4
		reconstruction	5
Bone	1	periosteum	1
		cortex	2
		through-and-through	3
		intra-articular	4
		major bone loss	5
Minor vascular	1	nonbleeding small hematoma	1
		nonbleeding large hematoma	2
		suturing	3
		ligation of isolated vessels	4
		ligation of named vessels	5

where:

- The percent injury to an organ wall probably indicates the portion of the entire circumference involved.

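### The primary analysis is not fixed to one outcome, and every test uses an unadjusted 5% level, so a civilian/combatant claim drawn from any of the five primary domains is not held at 5%

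*Combined protocol and SAP*

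**What the plan says.** The document describes the primary analysis in three ways.

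- **Five domains.** The Primary Objective in the opening summary and the Primary Measure in the body both list "Differences in injury mechanism, organs injured, surgical treatment given, postoperative complications and outcome between civilians" and combatants. No domain is ranked above another.
- **One labelled outcome.** Statistical Methods refers to "The difference in dichotomous, such as postoperative complication (primary outcome), and categorical outcomes", which singles out postoperative complication, but only in a parenthesis.
- **A different modelled outcome.** The same paragraph then specifies the adjusted regression models "with injury mechanism as the dependent variable and civilian/combatant as the main explanatory variable".

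Two secondary contrasts each repeat three of the domains. One is "Comparison of surgical treatment given, postoperative complications and outcome between patients with prior surgical treatment of their injury" and patients without it. The other is "Differences in surgical treatment given, postoperative complications and outcome between patients who receive surgical treatment less than 24 hours from injury" and patients treated later. Secondary Measures then sends the reader to the Patient Files list "for detailed primary and secondary measurements", without saying how many of those items will be tested.

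The only error-rate statement is "A 5% significance level will be used". Nothing in the document adjusts for multiple tests, orders them, or marks any of them as exploratory.

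**The concern.** The aim and the hypothesis call for a directional yes/no answer: do civilians have more extensive abdominal injuries than combatants? The plan does not say which result gives that answer. The outcome labelled primary, postoperative complication, does not directly measure injury extent. PATI does, and it is defined in the List of Definitions and Appendix 1, but neither the Primary Measure nor Statistical Methods names it.

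A report could therefore rest its conclusion on whichever of the five domains falls below 0.05 and still follow the plan as written. The false-positive risk of that conclusion would exceed the 5% stated. The Justification expects the findings to inform planning of surgical staff and facilities, so readers need to know which result was chosen in advance.

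**Working it through.** **Inputs from the document**

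- Level per test: 0.05, unadjusted (Statistical Methods).
- Civilian/combatant domains: 5 (Primary Measure).
- Domains in each of the two secondary contrasts: 3 (Secondary Measures), so 5 + 3 + 3 = 11 in all.
- Figure to reproduce: none beyond the 5% itself. The document gives no familywise error rate or power. The roughly 160 subjects are an expected case count from a convenience sample.

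**Assumptions.** There are no true differences, each domain gets one test, and each test has a true size of exactly 5%. The correlation between tests is unknown, so a range is shown.

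**Formula for independent tests:** P(at least one false positive) = 1 − (1 − 0.05)^m.

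- m = 1: 0.050
- m = 5: 1 − 0.95^5 = 0.226
- m = 11: 1 − 0.95^11 = 0.431
- m = 13: 1 − 0.95^13 = 0.487
- m = 14: 1 − 0.95^14 = 0.512
- m = 30: 1 − 0.95^30 = 0.785

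**Correlated tests.** These figures come from simulating two-sided z tests with equal pairwise correlation.

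| Tests | Independent | 0.3 | 0.5 | 0.8 |
|---|---|---|---|---|
| 5 (civilian/combatant) | 22.6% | 21.0% | 18.3% | 12.8% |
| 11 (all three contrasts) | 43.1% | 37.4% | 30.2% | 17.9% |
| 30 (assumed items) | 78.5% | – | 50.8% | – |

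**Which row answers which question.** Only the 5-test row describes a false civilian/combatant difference at domain level. The 11-test row is the chance of a false positive anywhere in the study.

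**The 30-test row is an assumption.** Counting what the document lists for the civilian/combatant contrast gives:

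- 2 cause and mechanism items;
- 14 organs (Appendix 1: "14 organs are examined");
- 5 procedures in the readable part of the case report form;
- 5 infection types;
- 7 others: other complication, intensive care, transfusion, further surgery, discharge status, re-admission and death.

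The sum is 2 + 14 + 5 + 5 + 7 = 33, taken as about 30. The plan does not say these items will be tested one by one.

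**The case against.** A reader might infer that a significant civilian/combatant difference somewhere is likely by chance alone. The documents do not support that, for three reasons.

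- **The secondary contrasts do not count towards it.** They compare patients by prior surgery and by time to surgery. Their six tests cannot produce a false civilian/combatant difference.
- **Five tests do not make it likely.** The chance is at most about 23%. It passes 50% only from 14 independent tests, and the plan specifies no such number. Appendix 1 sums the organs into one score, and mechanism is a single multi-category variable that would get one chi-square or Fisher test.
- **One outcome is labelled primary.** If the label on postoperative complication governs, that test is held at 5%.

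Two further points reduce the figures. Fisher's test is conservative for rare items: with an assumed 60 against 100 patients its true size is 0.8% at a 2% event rate and 3.4% at 10%, so the 79% for 30 items is an upper figure. The hypothesis is also directional. If only false positives favouring it counted, five independent tests would give 1 − 0.975^5 = 12%.

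It is also fair to say that formal adjustment across descriptive domains is a matter of judgement in a retrospective convenience sample.

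All of this limits the size of the problem but does not remove it. The parenthetical label does not confine the 5% level to that outcome. It conflicts with the five-domain Primary Measure and with the modelled outcome, and it leaves the injury-extent question to tests without error control. Even the 12% and 13% figures are more than twice the stated level.

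**Conclusion.** The point holds in this form: the document gives three incompatible accounts of what is primary and states no multiplicity control. For the civilian/combatant comparison at domain level, the chance of at least one false positive is about 13% to 23%, against a stated 5%. Study-wide, over 11 domain-level tests, it is about 18% to 43%. For an assumed 30 item-level tests it is about 51% to 79% (correlation 0.5 to independence), but that is what the open-ended measurement list permits, not what the plan prescribes.

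All figures assume no true differences and exactly 5% per test. The correlations are assumed, since the document gives nothing from which to estimate them. The defect does not invalidate the study, but it should be corrected because it determines what the study may conclude.

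**What to change.** Amend the Primary Objective, the Primary Measure and Statistical Methods so that all three name the same single primary outcome, and let only that outcome carry the 5% claim. There are two candidates:

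- postoperative complication, as Statistical Methods already labels it; or
- total PATI, which matches the stated aim of injury extent. First confirm that the operative records allow it to be scored.

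Fix the choice before the data are analysed, and make the dependent variable of the primary adjusted model agree with it. Report the other primary domains, all item-level results and both secondary contrasts as effect estimates with 95% confidence intervals, labelled exploratory and without significance claims.

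The cost is wording in three places and no new data collection if complication is kept. The downside is that no confirmatory claim can be made for the other domains.

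Holm's procedure across domains is optional. If one primary outcome is tested at 5% and four further domains are tested by Holm at another 5% without gatekeeping, overall error is 1 − 0.95 × (1 − 0.05/4)^4 = 9.7% for independent tests. Adjustment also costs power. With an assumed 80/80 split and rates of 30% against 50%, power is 74% at the 5% level and 50% at 1% (0.05/5). With an assumed 40/120 split it is 63% and 39%.

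### The hypothesis concerns extent of abdominal injury, but the outcome labelled primary is postoperative complication, the adjusted model as written has injury mechanism as its outcome, and no extent measure is named as primary

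*Combined protocol and SAP*

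**What the plan says.** **Question.** The Aim of Study is "To assess whether civilians have more complex abdominal injuries than combatants in an urban battle characterized by the use of indiscriminate weapons". The Justification hypothesises that the use of indiscriminate weapons in an urban setting "causes more extensive abdominal injuries to the civilian population than to combatants". The synopsis states the same aim in terms of extent.

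**Measures.** The Primary Measure section lists five domains without ranking them: injury mechanism, organs injured, surgical treatment given, postoperative complications and outcome. The Secondary Measures section compares treatment, complications and outcome by prior surgery and by delay (under or over 24 hours). It then points to the Patient Files list for detail.

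**Analysis.** Statistical Methods labels one outcome primary: "The difference in dichotomous, such as postoperative complication (primary outcome), and categorical outcomes with more than two categories" are to be tested by chi-square or Fisher test. Continuous variables get a t-test, with no variable named. Adjusted models are linear, logistic, ordinal or multinomial, "according to the nature of the outcome (continuous, binary, ordinal or nominal", and yet "with injury mechanism as the dependent variable and civilian/combatant as the main explanatory variable". Parameters such as "geographical location, date, age, sex, and injured organs, will then be included in the model as potential confounders".

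**PATI.** The index is in the List of Definitions. Appendix 1 gives its organ table, summation rule and threshold of 25. The Patient Files list cites Appendix 1 for the definition of operative findings. PATI is not named in the objectives, the primary or secondary measures, or Statistical Methods.

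**Size.** "It is expected that approximately 160 subjects will be enrolled", as a convenience sample with no power calculation.

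**The concern.** The hypothesis is about how badly the abdomen was injured. The outcome labelled primary lies downstream of that, and the outcome fixed for the adjusted model lies upstream. Neither measures extent.

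Two wrong conclusions become possible. A difference in complications could be reported as support for the hypothesis although the injuries were alike, for instance because one group arrived later or had more often been operated on elsewhere. Equally, a null result on complications would not exclude a real difference in injury. The adjusted result, as written, would describe which mechanism each group met and not the damage it did.

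The data are retrospective and several measures could stand for extent. If none is fixed beforehand, the choice can follow the results.

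**Working it through.** The plan has no power figure to reproduce. The expected 160 is a forecast of available cases (160/1,800 = 8.9% of the database). The check is mainly one of consistency.

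**1. Each element against the hypothesis**

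| Element | Section | Relation to extent |
|---|---|---|
| More extensive or complex injury | Justification, Aim of Study | Is extent |
| Postoperative complication, labelled primary | Statistical Methods | Downstream |
| Injury mechanism, dependent variable | Statistical Methods | Upstream |
| Injured organs, potential confounder | Statistical Methods | Component of extent |
| Organs injured, surgical treatment given | Primary Measure | Bear on extent; unranked, no summary measure stated |
| PATI | List of Definitions, Appendix 1 | Measures extent; no comparison specified |

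**2. The model sentence, read two ways**

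- *Literally.* Injury mechanism is the only dependent variable. It is nominal, so linear, logistic and ordinal models have no use for it as listed. Complication and extent get no adjusted analysis.
- *As a slip, with every outcome meant.* Complication gets its logistic model, but the suggested covariates put injured organs into an extent model.

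**3. What adjusting for injured organs would do.** From Appendix 1, PATI = Σ I(k) × r(k) × g(k), where I(k) is 1 if organ k is injured, r(k) is its risk factor and g(k) its injury estimate. Holding every I(k) fixed leaves only differences in g(k). If civilians have more organs hit but the same mean grade for each injured organ, whatever else is injured, the adjusted difference is zero although the injuries are more extensive. If the groups differ only in grade, the difference remains. What adjustment removes therefore runs from nothing to all of it.

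**4. Complication differing with identical injuries.** All inputs here are assumed. Let the share delayed or previously operated on be s1 and s2, with risk a without and b with that factor. The difference in complication is (s2 − s1) × (b − a).

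- Shares 30% and 50%, risks 25% and 50%: 0.20 × 25 = 5.0 points.
- Shares 20% and 60%, risks 20% and 60%: 0.40 × 40 = 16.0 points.

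The documents give neither shares nor risks. This shows only that the route exists.

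**5. Precision for an extent outcome.** Assumed: two-sided 5%, 80% power and the split; the total of 160 is from Sample Size. Detectable difference in SD units = (1.96 + 0.84) × √(1/n1 + 1/n2).

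- 64/96: 2.80 × √(1/64 + 1/96) = 2.80 × 0.1614 = 0.45
- 80/80: 2.80 × 0.1581 = 0.44
- 48/112: 2.80 × 0.1725 = 0.48
- 32/128: 2.80 × 0.1976 = 0.55

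**The case against.** **Extent is already among the primary measures.** This stands in part. Organs injured is listed, and so is surgical treatment given, which matters because Appendix 1 grades severity partly by treatment (splenectomy, nephrectomy, ligation). A reader might infer that the plan never examines extent; the documents do not support that. But the five domains are unranked, and the primary label goes to complication.

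**PATI is within reach.** Also true. Secondary Measures refers to the Patient Files list, that list cites Appendix 1, and the t-test sentence could be applied to a score. That route permits a PATI comparison but commits to none. Nor can it be inferred that PATI will not be captured: CRF items 25 to 28 are not visible in the text available, so this cannot be judged.

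**The mechanism wording is a slip.** Probably so, since four model types cannot be meant for one nominal variable. It would be too strong to say that the investigators intended to model mechanism alone. The sentence still has to be corrected, and the covariate question then arises. The covariates are introduced as examples and as potential confounders, so they are not a fixed set, and injured organs is a plausible covariate for a complication model.

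**Complication is a fair proxy, and mechanism is relevant.** Appendix 1 does link complications to PATI above 25, and the Justification says "The use of these indiscriminate weapons could affect civilians to a greater extent than combatants", which mechanism addresses. Both are reasons to keep these outcomes. Neither makes them a direct test of extent.

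**Low power on complication proves the defect.** This reading is tempting, but the documents give no PATI distribution or complication risk. Any simulated power would rest wholly on assumptions and is not evidence here.

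**Conclusion.** The point holds on the text and should be settled before analysis. The labelled primary outcome does not measure what the hypothesis is about, and the adjusted model as written does not either. Under the literal reading, no extent measure has an adjusted analysis; under the generous reading, an extent model could be adjusted for part of its own outcome.

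The conclusion is limited to that. Two listed primary measures bear on extent and PATI is defined; what is missing is one extent measure named as primary, with its comparison and model.

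The mismatch itself depends on no numerical assumption. The only size offered is precision: about 0.45 SD detectable at an assumed 64/96 split, and 0.44 to 0.55 SD over civilian shares from 50% to 20%. A smaller true difference would often be missed whichever extent score is used.

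**What to change.** 1. **Primary outcome.** In Primary Measure and Statistical Methods, name one injury-extent measure, civilians versus combatants. Use total PATI if a check made before any group comparison shows that it can be scored from the operative records; otherwise use the number of injured organs. Report the difference with a 95% confidence interval and the number scorable in each group.
2. **Model sentence.** Suggested wording: *Each outcome will be the dependent variable of its own regression (linear, logistic, ordinal or multinomial, according to its type), with civilian/combatant status as the main explanatory variable. The model for injury extent will not be adjusted for injured organs.* Because the List of Definitions builds the groups largely from age and sex, show results with and without those two covariates.
3. **Secondary outcomes.** Keep postoperative complication and injury mechanism as secondary outcomes, each with its own model.

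**Cost.** Text changes in two sections and a scoring check; no new patients. There are four downsides. Complication is no longer the headline outcome. Some PATI grades reflect the treatment given as well as the injury. Findings from a first operation elsewhere may be missing for referred patients. The organ count would miss a difference that lies only in grade.

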Penetrating abdominal injury	An injury penetrating the peritoneum into the abdominal cavity
Peritonitis	Rigid involuntary general tenderness of the abdominal wall.
Postoperative complication	Any deviation from the ideal postoperative course that is not inherent in the procedure and does not comprise a failure to cure. Classification of Surgical complications will be done according to Clavien-Dindo (appendix 2).
SSI	Surgical Site Infection is present when one of the following criteria are met: i. Purulent discharge from surgical site ii. Positive culture iii. Surgical site requires reopening iv. SSI is present as judged by attending physician Severity according WHO guidelines (appendix 3).

Background

Trail location

In 2014, Islamic State Group (ISg) made significant territorial gains in several governorates in Iraq and captured key cities, including Fallujah and Mosul¹. ISg is unique among terrorist groups in that it employs a combination of conventional maneuverer warfare with tactics such as human shields, improvised explosive devices (IED's), suicide bombers and drones in order to capture and hold territory. These tactics are indiscriminate, leading to excessive civilian casualties².

Emergency Hospital (EH) is one of two trauma hospitals in Erbil, a major metropolitan area in Kurdistan Region of Iraq. Erbil is located 94 kilometres east of the city of Mosul. Mosul is the provisional capital of the Nineveh region of Iraq. In mid-October 2016, the offensive to liberate Mosul from the ISg was initiated. EH was assigned by the Governate to exclusively provide care to injured from the armed conflict in and around Mosul. Since late December 2016 treatment facilities, run by other emergency care providers, have opened closer to Mosul. EH since then mainly served as a referral hospital.

The battle of Mosul formally ended on 10 July, 2017. The admission of casualties from Mosul to EH has since then diminished significantly. NGOs and other emergency care providers have also decreased their activities since.

Previous reports on exploratory laparotomy in conflict settings

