Appendix 3: Surgical Site Infection defined by WHO¹³

- Superficial incisional, affecting the skin and subcutaneous tissue. These infections may be indicated by localized signs such as redness, pain, heat or swelling at the site of the incision or by the drainage of pus.
- Deep incisional, affecting the fascial and muscle layers. These infections may be indicated by the presence of pus or an abscess, fever with tenderness of the wound, or a separation of the edges of the incision exposing the deeper tissues.
- Organ or space infection, which involves any part of the anatomy other than the incision that is opened or manipulated during the surgical procedure, for example joint or peritoneum. These infections may be indicated by the drainage of pus or the formation of an abscess detected by histopathological or radiological examination or during re-operation. Organ infection is not included within the scope of this guideline.

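### The unadjusted test for outcomes with more than two categories ignores order, although the protocol defines two ordered scales, and the ordinal model for the adjusted step is not clearly assigned to either

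*Combined protocol and SAP*

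**What the plan says.** - **Unadjusted comparison (Statistical Methods).** Dichotomous outcomes, with postoperative complication labelled as primary, and "categorical outcomes with more than two categories will be tested using chi-square or Fisher test". Continuous variables get a t-test. No rank or trend test is named.
- **Adjusted comparison (same paragraph).** The plan will use "linear, logistic, ordinal or multinomial regression models, according to the nature of the outcome (continuous, binary, ordinal or nominal", but "with injury mechanism as the dependent variable and civilian/combatant as the main explanatory variable".
- **Ordered scales.** The List of Definitions classifies postoperative complications by Clavien-Dindo (Appendix 2, grades I to V). For SSI it adds "Severity according WHO guidelines (appendix 3". Appendix 3 runs from superficial incisional, through "Deep incisional, affecting the fascial and muscle layers", to organ or space infection.
- **Error rate and size.** "A 5% significance level will be used". "It is expected that approximately 160 subjects will be enrolled", and "the sample size will be a convenience sample of the available cases during the study period". No power, target effect, outcome distribution or civilian/combatant split is given.
- **Data capture.** CRF item 31 records infection by layer. Several marks are allowed, and sepsis and unspecified infection are also options. Item 32 records other complications as present or absent, with type and measures taken in free text.

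**The concern.** A chi-square or Fisher test on K categories gives the same p-value if the categories are shuffled. It asks whether the two patterns differ in any way, and spreads the evidence over K-1 degrees of freedom. Where one group is consistently worse, a test that uses the order puts that evidence on one degree of freedom and is more likely to detect it.

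Postoperative complications and outcome are compared in the primary objective and in both secondary ones (prior surgery; surgery before or after 24 hours). The sample is fixed, so lost power cannot be regained by recruiting. At stake is that a real shift in grade or depth is reported as no significant difference. In addition, the unadjusted and adjusted results for one outcome could disagree because only one of them uses the order.

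**Working it through.** The plan has no power figure to reproduce.

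**1. Which test reaches an ordered outcome?**
- *Unadjusted step:* only chi-square or Fisher, in all three contrasts.
- *Adjusted step, read literally:* the dependent variable is injury mechanism (gunshot, stab, blast and so on), which is nominal. No ordered outcome is modelled.
- *Adjusted step, read charitably:* the model follows the type of outcome, so grade and depth would get ordinal regression. The sentence still names only civilian/combatant as main explanatory variable, so nothing is expressly assigned to the secondary contrasts.

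**2. Cost of the extra degrees of freedom.** Power = P(noncentral χ² with df and λ > 95% point of central χ² with df). Put all the signal in the trend and choose λ so that the 1-df test has 80% power: λ = 7.85. With the same λ:

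| df | Power | Loss, points |
|---|---|---|
| 3 (four levels) | 64.5% | 15.5 |
| 5 (six levels) | 55.5% | 24.5 |
| 7 (eight levels, IIIa/b and IVa/b split) | 49.3% | 30.7 |

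**3. Simulation at N = 160.** From the plan: N and the 5% level. Assumed: two-sided testing, an 80/80 or 56/104 split, the category percentages, and a common odds ratio θ, where odds of category j or worse in group 2 = θ × the same odds in group 1. Group 2, the larger when the split is unequal, is the worse one.

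Example with θ = 2 and 65/15/10/10% (none, superficial, deep, organ/space): odds of any infection 0.35/0.65 = 0.538 become 1.077, or 51.9%. Deep or worse goes from 20% to 33.3%, and organ/space from 10% to 18.2%.

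Power in %, Pearson chi-square v tie-corrected Wilcoxon-Mann-Whitney, 20,000 replicates:

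| Scale, group 1 % | Split | θ = 1.5 | θ = 2 | θ = 2.5 | θ = 3 |
|---|---|---|---|---|---|
| Infection 65/15/10/10 | 80/80 | 16.4 v 25.1 | 44.2 v 61.7 | 72.2 v 85.8 | 87.6 v 95.4 |
| | 56/104 | 13.5 v 23.5 | 37.7 v 56.4 | 64.8 v 82.0 | 83.1 v 93.4 |
| Infection 75/10/7/8 | 80/80 | 13.9 v 21.6 | 37.4 v 54.6 | 64.0 v 80.1 | 82.1 v 92.4 |
| | 56/104 | 10.5 v 19.2 | 30.4 v 49.6 | 56.0 v 75.4 | 76.5 v 89.7 |
| Grade 45/10/15/12/8/10 | 80/80 | 14.9 v 29.0 | 41.7 v 67.8 | 69.1 v 89.5 | 86.2 v 97.1 |
| | 56/104 | 12.8 v 27.1 | 37.1 v 63.7 | 62.9 v 86.5 | 81.8 v 95.8 |

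The differences run from about 8 to 19 points (infection) and 11 to 27 (grade). Runs of 3,000 replicates reached 20 and 28, so I carry 8 to 20 and 11 to 28. At θ = 1.25 or 4 the loss is only about 1 to 5 points. With θ = 1 both tests reject in 4.6 to 5.2%.

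**4. Sensitivity.**
- If the smaller group (56) is the worse one, the losses are about 6 to 15 points (infection) and 11 to 24 (grade).
- Other assumed distributions, with splits out to 40/120, gave about 6 to 28 points for four levels, 11 to 29 for six and 15 to 39 for eight.
- *Superficial only* (65/15/10/10 to 50/30/10/10, 80/80): chi-square 48.9% v Wilcoxon 31.2%.
- *Death only* (grade V from 10% to 25%, the other categories scaled down in proportion, 80/80): 45.2% v 40.8%, in favour of chi-square.
- *Depth worse, share infected unchanged* (65/25/5/5 to 65/10/12.5/12.5, 80/80): 78.9% v 10.4%, in favour of chi-square.

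**The case against.** The strongest reply has four parts.

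*The primary outcome is safe.* Statistical Methods treats it as dichotomous, and order cannot matter in a 2×2 table. This stands. A reader might infer that the declared primary analysis is underpowered because of this rule; it is not.

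*The plan already has ordinal regression.* In part. A reader might infer that every outcome with more than two categories is analysed without regard to order throughout. The paragraph does not support that: it recognises ordinal outcomes in the adjusted step, which matters more in a confounded cohort. What it does not do is make an ordered outcome the dependent variable.

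*Comparing grade or depth is implied, not spelled out, and no direction is claimed for it.* The Patient Files list has infection and other complication as yes/no/unknown with a pointer to the appendices. The objectives speak of differences. The directional hypothesis concerns the extent of abdominal injury, for which the protocol defines a 0 to 200 index. This stands, so the point bites only when grade or depth is compared. On the four-level infection scales the gain over a plain yes/no test is also small: at 80/80 and θ = 2, 61.7% v 56.7% and 54.6% v 53.1%. For six-level grade it is larger, 67.8% v 55.3%.

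*The ordered test is not always better.* This stands. The death-only case shows that chi-square can win even when every change is for the worse, so it would be wrong to say that the advantage disappears only when the groups differ without a consistent shift.

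**Conclusion.** The point holds for the unadjusted comparison of ordered outcomes. The plan defines two ordered scales and assigns them a test that cannot use the order. The adjusted step is worded so that it is unclear whether either scale is modelled as ordered, above all in the secondary contrasts.

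The size is conditional: roughly 8 to 20 points of power for four-level infection depth and 11 to 28 for six-level grade. This rests on N = 160, the assumed distributions, an 80/80 or 56/104 split with the larger group worse, and a common odds ratio of 1.5 to 3. A reader might take one such range as a property of the plan. The documents do not support that, since they give no split, distribution or effect, and under other assumptions the loss is smaller, larger or reversed. It is a worthwhile, inexpensive improvement to the comparisons of severity and not a threat to the primary result.

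**What to change.** In Statistical Methods, before the analysis:

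1. Limit chi-square/Fisher to dichotomous and nominal outcomes (for example cause and mechanism of injury).
2. Add: *Worst Clavien-Dindo grade per patient and worst SSI depth per patient (none < superficial < deep < organ/space) will be compared with the Wilcoxon-Mann-Whitney (linear-by-linear) test. They will be adjusted with a proportional-odds model that has the ordered outcome as dependent variable and the group contrast as main explanatory variable, for the primary and both secondary contrasts.*
3. Reword the clause that makes injury mechanism the dependent variable, so that each model names its own outcome.
4. State where sepsis and unspecified infection on CRF item 31 fall relative to the depth scale, and how grade is derived from items 31 to 34, 36 and 40. The CRF pages available show no grade field.
5. Report the percentage in each category by group.

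The cost is a few sentences and a little derivation work; no new data are needed. The downside is lower sensitivity to a difference that is not a consistent shift, which the tabulated percentages would still show.
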